SECONDARY: Microbial translocation [Primarily, Lipopolysaccharide binding protein (LBP)], zinc level, oxidative markers, safety measures (% subjects with >Grade 2 adverse events possibly or probably to study drugs), lipid levels, insulin resistance (HOMA-IR), endoPAT, and blood pressure.

Design and Outcomes:

This is a pilot open labeled randomized double arm study, studying the efficacy and safety of Zinc therapy on cardiovascular outcomes in ≥ 18 years old HIV-infected patients, on stable ART (for at least 12 weeks) and with zinc levels ≤ 0.75 mg/L in the last 60 days.

Subjects will be evaluated and data will be collected according to the following schedule:

Evaluation (Weeks)	Screen	Entry*	Wk 4	Wk 10	W 16 or premature study discontinuation
Written consent form	X				
Inclusion/exclusion	X				
Family history of CVD/diabetes/HTN		X			
CVD Risk Score		X			X
Targeted physical exam/weight/blood pressure	X	X	X	X	X
Compliance assessment/safety monitoring			X	X	X
Smoking, illicit drugs and alcohol status		X			X
Dietary logs and Activity status		X			X
Height	X				
Hematology/chemistries	X	X	X	X	X
Urine β -HCG (women)	X	X	X	X	X
Fasting lipoprotein profile		X			X
Fasting insulin, glucose, HOMA-IR		X			X
Plasma inflammation markers		X			X
Microbial translocation (IFAB, LBP)		X			X
Oxidative markers		X			X
Zinc levels	X	X			X
Calcium Score		X			
DEXA		X			
Endothelial function		X			X
Resting Energy Expenditure (REE)		X			X
Stored fasting plasma, serum, urine and stool ***	X	X	X	X	X

Intervention and Duration:

The duration of the study will be 16 weeks. Patients will be given zinc gluconate capsules at a dose of 45 mg, or 90 mg, elemental zinc daily for 16 weeks. No additional follow up will occur after 16 weeks.

Sample size and population:

The total sample size is 50 patients, 25 patients will be randomized to one (45 mg) capsules and 25 patients will receive two 45 mg capsules (or 90 mg).

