- HIV-1 infection as documented by any licensed ELISA test kit and confirmed by Western blot at any time prior to study entry. HIV-1 culture, HIV-1 antigen, plasma HIV-1 RNA, or a second antibody test by a method other than ELISA is acceptable as an alternative confirmatory test
- Male or Female age ≥ 18 years
- Zinc level ≤ 0.75 mg/L *in the last 60 days*
- Receiving a stable antiretroviral regimen for at least the last 12 weeks prior to study entry
- Cumulative duration of antiretrovirals for at least 6 months at study entry
- Provides written informed consent and is capable of reading and comprehending the informed consent
- All women of child-bearing potential (WOCBP) must have a negative serum or urine pregnancy test (minimum sensitivity 25 IU/L or equivalent units of HCG) within 72 hours prior to start of study medication. WOCBP is defined as any female who has experienced menarche and who has not undergone successful surgical sterilization (hysterectomy, bilateral tubal ligation, or bilateral oophorectomy), who is not postmenopausal (defined as amenorrhea ≥ 12 consecutive months), or is on hormone replacement therapy (HRT) with documented plasma follicle-stimulating hormone level 35 mIU/mL. Women who are using oral, implanted, or injectable contraceptive hormones or mechanical products such as an intrauterine device or barrier methods (diaphragm, condoms, spermicides) to prevent pregnancy or practicing abstinence or where partner is sterile (e.g., vasectomy), should be considered to be of child bearing potential.
- Female subjects who are not of reproductive potential (have reached menopause or undergone hysterectomy, bilateral oophorectomy or tubal ligation) or whose male partner has undergone successful vasectomy with resulting azoospermia or has azoospermia for any other reason, are eligible without requiring the use of contraception. Acceptable documentation of menopause, sterilization, and azoospermia is patient reported history.
- All subjects must not participate in a conception process (e.g. active attempt to become pregnant or to impregnate, sperm donation, in vitro fertilization), and if participating in sexual activity that could lead to pregnancy, the female subject/male partner must use condoms (male or female) in addition to one of the following forms of contraception while on study: either a spermicidal agent, diaphragm, cervical cap, IUD, or hormonal-based contraception.

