- For any Grade 4 toxicity (confirmed X 2 values for laboratory abnormalities) regardless of the cause, subjects will be taken off study drugs but will continue to be followed and undergo the evaluations as per schedule of events. Exceptions are asymptomatic elevation of indirect bilirubin in subjects receiving indinavir or atazanavir therapy, asymptomatic elevation of CPK, or elevations in lipid levels.

CRITERIA FOR PERMANENT STUDY DISCONTINUATION

-Request by the subject to withdraw

-At the discretion of the IRB

-Pregnancy or breast-feeding

[figure not shown]
-Request of the primary care physician if s/he thinks the study is no longer in the best interest of the subject.

STATISTICAL CONSIDERATIONS

The primary Aim of this pilot study is to demonstrate that oral dosing of zinc can impact a biological signature in patients with HIV. Biological signatures (hs-CRP, sCD14, sTNF-RI, LBP) will be assessed to determine if giving the natural product (zinc gluconate at 45 mg and 90 mg) to patients with HIV results in a meaningful change in the measure.

Inter-assay variability less than 15% are generally acceptable¹¹. To reduce this variability we will repeat each of these assays twice (run in duplicate) and compute average from the repeated assays performed in the same lab under same conditions conducted by the same technician. Given this set-up, the bioassays will efficiently quantify the biomarkers with less than 6% inter-assay variability which is substantially less than the general acceptable guidelines. Moreover, this inter-assay variability should be equivalent in both sets of measures obtained at baseline and after the Zinc supplementation.

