We hypothesize that the distribution of at least two of the four biomarkers of primary interest (hs-CRP, sCD14, sTNF-RI and LBP) will be shifted towards left after oral supplementation compared to the baseline distribution of the biomarker, see the Figure below. This shift/change in the distribution is primarily due to the location change of a biomarker. Since the random or nuisance variations are same (although nominal) in both distributions, we will perform hypothesis tests for the systematic change in the distributions due to the treatment. We will perform Kolmogorov–Smirnov (K-S) test for the differences in distributions and median test for location change. These tests will determine significant effects of zinc supplementation on the targeted biomarkers. The K-S and median tests are global test for overall significance. We will also look at the effect of zinc supplementation on individual level.

To elicit treatment effects on each individual, we will subtract baseline value of a biomarker from the post zinc supplementation measured value of the biomarker (post minus pre). The baseline subtracted values of biomarker will have either zero (no change), positive or negative values. The baseline corrected biomarker values are in continuous nature, basically the subtracted values on the real line. For measuring significance of treatment by controlling random errors, we will perform linear regression on the baseline corrected biomarker values. This analysis has similarity with the Microarray normalization method using iterative linear regression¹². The significant regression coefficient (intercept only) would indicate that the difference is due to the zinc supplement.

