Further, for individual level impact of zinc supplementation, we will create categorical variable from the baseline subtracted biomarker values. Let's denote the number of positive, negative, and no change biomarker values by n_1 , n_2 , and n_3 , respectively, for a biomarker. Note that the total sample size $n = n_1 + n_2 + n_3$. From this count we will compute proportions of positive, negative, and no changes. We hypothesize that most of the subtracted values will be negative. Since we want to look at the benefit of supplementation, we will compare the proportions of negative values to the proportions of positive values using McNemar's test statistic¹³. For this moderate sample size without placebo trial, we will estimate the 90% confidence interval for the proportions difference using Agresti and Min¹⁴ methods. We will also perform logistic regression analysis on the binary change (positive vs negative) to estimate the odds ratio for the benefit of zinc supplementation. From the estimated logistic regression model will be able to predict probability of negative change (reduction in inflammation) for receiving zinc supplementation.

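### The plan attributes a significant change from entry to zinc in advance, and promises an odds ratio for its benefit, although every patient is assigned zinc

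*Combined protocol and SAP*

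**What the plan says.** All citations are to the combined protocol and SAP.

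- **Aim (Statistical Considerations).** The section opens with this statement: "The primary Aim of this pilot study is to demonstrate that oral dosing of zinc can impact a biological signature in patients with HIV". The primary objective in the Précis and under Study Objectives likewise asks whether zinc affects inflammation markers, to be answered by following changes over time and correlating them with changes in zinc level.
- **Distribution tests (Statistical Considerations).** The plan says "we will perform hypothesis tests for the systematic change in the distributions due to the treatment", using Kolmogorov–Smirnov and median tests, and adds: "These tests will determine significant effects of zinc supplementation on the targeted biomarkers".
- **Individual change (same section).** Post-minus-pre values are presented as showing each person's treatment effect and go into an intercept-only linear regression: "The significant regression coefficient (intercept only) would indicate that the difference is due to the zinc supplement".
- **Logistic regression (same section).** The sign of the change is modelled "to estimate the odds ratio for the benefit of zinc supplementation", and the model is then used to "predict probability of negative change (reduction in inflammation) for receiving zinc supplementation". No predictor is named.
- **Allocation (Sample size and population; Study Design).** "25 patients will be randomized to one (45 mg) capsules and 25 patients will receive two 45 mg capsules (or 90 mg". Statistical Considerations itself notes that there is no placebo.

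**The concern.** A test of mean change from entry asks whether the marker moved. It cannot say why. With no concurrent patients off zinc, a shift caused by zinc and a shift of equal size caused by anything else over 16 weeks give the same data. The plan nevertheless fixes the causal reading in advance, on the analysis that serves its primary aim. Followed as written, it would allow a significant change from any cause to be stated as a zinc effect. The error can also run the other way: an unfavourable drift could hide a real effect.

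The odds ratio is a separate fault that does not depend on drift. A zinc odds ratio needs a no-zinc reference, and the trial has none. Whatever the model returns would carry a label it does not support.

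**Working it through.** **1. What the intercept estimates.** For patient i, post minus pre = (zinc effect) + (all other change over 16 weeks) + (error). The intercept estimates the mean of the first two terms together. All 50 patients (25 + 25) are on zinc, so no contrast in the trial separates them.

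**2. Whether the plan's own argument closes the gap.**

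| Safeguard | Where | What it covers |
|---|---|---|
| Duplicate assays; equal inter-assay and nuisance variation before and after | Statistical Considerations | Measurement error |
| Samples batched and assayed at the end | Study Entry procedures | Assay drift |
| "Receiving a stable antiretroviral regimen for at least the last 12 weeks prior to study entry", 6 months' cumulative ART, HIV-1 RNA at or below 400 copies/mL | Inclusion Criteria | Part of real change |
| Limits on recent inflammatory illness, hospitalization and inflammation-affecting agents | Exclusion Criteria | Part of real change |
| Visits postponed for acute illness | Timing of Evaluations; Statistical Considerations | Part of real change |
| Correlation with change in zinc level | Study Objectives | A non-randomised association |

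None is a concurrent control. ART changes are to be allowed for by a method that is not stated (Study Design). Diet, activity and substance use are recorded at entry and week 16, but no stated analysis uses them. An intercept-only model has no term for any of these.

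**3. What each possible logistic model gives.**

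- Intercept only: exp(b0) = (number falling)/(number rising). This is an odds, a before/after quantity.
- Arm as predictor (data are exported as arm A and arm B, Blinding): exp(b1) is 90 v 45 mg.
- Change in zinc level as predictor: an observational association among treated patients.
- An indicator zinc = 1 for everyone: its column equals the intercept column, the design has rank 1 of 2, and the coefficient is not identified.

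None is a zinc-versus-no-zinc odds ratio.

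**4. The plan's own power figure.** Effect size consideration gives 80% power at n=20 for Cohen's d = 0.20, with a one-sided 0.10 paired t-test, in at least two of four markers. Per-marker power is 1 − F(t; n−1, d√n), where F is the noncentral t distribution function and t the 0.90 quantile on n−1 df. With t = 1.328 and d√n = 0.894 this is 34.2%. At least two of four, if independent, is 1 − (1−p)^4 − 4p(1−p)^3 = 42.3%. The 80% is not reproduced. That is a separate matter, and this point does not rest on it.

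**5. Illustration of drift.** The documents give no drift, so its size and direction are assumed, in SD of the differences, with zero zinc effect. The formula in step 4 applies with drift in place of d.

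| Drift | n=20 | n=40 |
|---|---|---|
| none | 10% | 10% |
| 0.1 favourable | 20% | 26% |
| 0.2 favourable | 34% | 49% |
| 0.3 favourable | 51% | 72% |
| 0.2 unfavourable | 1.6% | 0.6% |

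A true effect of 0.2 met by an unfavourable drift of 0.2 nets to zero and is found 10% of the time. For at least two of four markers, all drifting favourably by 0.2, the rates are 42% (n=20) and 67% (n=40) if independent, against 5% with no drift. With no drift in hs-CRP they are 32% and 52%. At an assumed between-marker correlation of 0.8, simulation gives about 38% and 54%, against about 11% with no drift.

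**6. Marker units.** A 0.2 SD drift is 0.2 × SD × √(2(1−ρ)), using the plan's baseline SDs, natural logs assumed, and an assumed entry to week-16 correlation ρ of 0.8 to 0.5. This is a fall of 4–7% in sCD14 and 5–7% in sTNF-RI, and 7–10% of the mean for LBP, but 27–42% of the mean for hs-CRP (SD 10.45, mean 4.95).

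**The case against.** The best defence is that this is a disclosed exploratory pilot without placebo, in stable patients selected on zinc level rather than on the biomarkers, so drift may be small. That stands as a defence of the design. It does not defend a sentence that turns significance into causation, and pilot status is a reason for more cautious wording.

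Three further objections stand in part.

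- **The drift figures are assumed.** They restate the power curve with drift in place of effect, and 0.2 is the plan's own target effect. They also borrow the one-sided 0.10 level, which is stated only for the sample-size paired t-test. No level is given for the intercept regression, Kolmogorov–Smirnov or median tests. At two-sided 0.10 the favourable-direction rates at 0.2 drift are 22% (n=20) and 34% (n=40). The fault in the inference needs none of these figures.
- **A reader might infer that the logistic regression cannot be fitted at all.** The documents do not support that. Three of the four models in step 3 are estimable; what fails is the label and the missing predictor.
- **A reader might also count the predicted probability of a fall as an error.** It is not. It is the proportion falling among treated patients, and it can be estimated.

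**Conclusion.** The point holds. The interpretation rule for the change-from-entry tests is wrong as written, because every patient is assigned zinc and no stated safeguard supplies a comparison. The promised odds ratio has no named predictor, and none available would give it the stated meaning. This conclusion rests only on the allocation and the plan's wording.

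The 34% and 49% figures indicate how much could be misattributed under an assumed 0.2 SD drift. They are not an estimate of this trial's false-positive rate, and nothing in the documents shows that drift of that size will occur. Nor do the documents support inferring that the single-treatment pilot is invalid or must add a placebo arm: a change-from-entry study can be reported honestly as one. Correcting the wording should come before analysis, since it bears on the primary aim and sets what the trial may conclude.

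**What to change.** 1. In Statistical Considerations, replace the causal sentences on the intercept and on the Kolmogorov–Smirnov and median tests. Do the same for the attribution of the distribution shift to treatment and the description of individual differences as treatment effects. Suitable wording: a significant result indicates a change from entry to week 16 during zinc treatment, which cannot be attributed to zinc without a concurrent control. Align the aim in that section and the objectives in the Précis and Study Objectives, which otherwise keep the same causal claim.
2. Replace the odds ratio for zinc with the proportion (or odds) of patients with a fall and its 90% CI. Alternatively, name arm as the predictor and label the ratio 90 v 45 mg. Keep the predicted probability, described as applying to treated patients.

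Neither change needs a new patient, visit, arm or assay. The cost is a more modest conclusion and openly imprecise estimates. If 60% fall (assumed), the Wilson 90% CI is 0.42–0.76 at n=20 and 0.47–0.72 at n=40. With 60% falling in each arm, the 90 v 45 mg odds ratio has a 90% CI of a factor exp(1.645 × √(2/(m × 0.6 × 0.4))) each way: 2.9 at m=20 per arm, 2.6 at m=25.

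An adjusted between-dose comparison, and a sensitivity analysis without patients whose ART changed, are optional and not part of this point.

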Effect size consideration: As above, we previously stated that we will perform significance tests for the shift of distributions of biomarkers after the zinc supplementation using Kolmogorov-Smirnov (K-S) test. The amount of shift or effect size will be measured using Cohen's d value. For estimating the effect size, we used our statin study data as the preliminary data (NCT01218802). In the statin study the baseline mean (SD) of hs-CRP, log(sCD14), log(sTNF-RI), and LBP are 4.95(10.45), 7.71 (0.35), 7.46 (0.37), and 21.11(10.91), respectively. For each level of zinc supplementation (i.e. 45 mg or 90 mg zinc) we will compute the change in a biomarker by taking the difference of a biomarker measured before- and after- the zinc supplementation. For example, we will compute the difference in LBP measured at baseline and after the zinc supplementation. Similarly, differences will be computed for the other biomarkers. The sample size of 20 achieves 80% power to detect effect size (Cohen's $d = \text{mean difference}/\text{SD of differences}$) of 0.20 or higher using a paired t-test with a 0.10 one-sided significance level in at least two biomarker out of the four. For the combined sample size of $n=40$ (both doses combined), the estimated effect size should be higher than the threshold Cohen's $d = 0.20$. The effect size estimation is performed using nQuary Advisor 7.0 software¹⁵.

All analysis will be by intent to treat. All subjects, regardless of whether they remain on study drug, will continue to be followed throughout the duration of the study. It is standard practice in the HIV studies where inflammation markers are measured, that every attempt would be made to schedule study visits during a time that subjects are not acutely ill. That would mean that a visit would be rescheduled if a patient shows up sick, as acute illnesses may affect inflammation markers. A period of >7 days ill-free would be required. This happens rarely overall but if it does in the setting of this study, participants would be asked to come back after illness resolves.

HUMAN SUBJECTS

Institutional Review Board (IRB) Review and Informed Consent

This protocol and the informed consent document and any subsequent modifications will be reviewed and approved by the University Hospitals Cleveland Medical Center CWRU IRB. A signed informed consent form will be obtained from each study subject. The informed consent form will describe the

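### The stated 80% power (n = 20, d = 0.20, at least two of four biomarkers) does not reproduce: with all four markers shifted it is about 35% to 42%, and it cannot exceed 68%

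*Combined protocol and SAP*

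**What the plan says.** The sample size justification is in the Effect size consideration paragraph of the Statistical Considerations. Changes are to be computed separately for each dose, and then: "The sample size of 20 achieves 80% power to detect effect size" "of 0.20 or higher using a paired t-test with a 0.10 one-sided significance level in at least two biomarker out of the four". Cohen's d is defined there as the mean difference divided by the SD of the differences. For the two doses pooled (n = 40) the paragraph gives no power. It says only that "the estimated effect size should be higher than the threshold" of 0.20.

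The success rule matches the hypothesis earlier in the same section: "We hypothesize that the distribution of at least two of the four biomarkers of primary interest" (hs-CRP, sCD14, sTNF-RI and LBP) will move to lower values. The Study Design section plans 50 patients, 25 per dose. The documents give no correlation between the biomarkers' changes.

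**The concern.** A standardized paired effect of 0.20 is small, and 20 pairs is few. Even with a one-sided 0.10 test, one comparison of this kind has power well below one half. Requiring two significant results out of four cannot lift that to 80% unless each marker already has fairly high power.

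What is at stake is how the result is read. Against a stated 80% power at d = 0.20, a trial in which fewer than two markers reach significance would be taken as fair evidence that zinc has no effect of that size. If the real power is about 40%, such a result is the more likely outcome even when all four markers do shift by that amount. The same figure would feed any decision on whether and how large to make a follow-on study.

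**Working it through.** **Inputs, all from the Statistical Considerations:** n = 20 per dose; d = 0.20 on the SD of the differences, so no pre-post correlation is needed; paired t-test; one-sided alpha 0.10; success = at least two of four biomarkers significant. The between-marker correlation is not given, so a range is shown.

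**Step 1: one biomarker.** Power is p = P(T′ > t₀.₉₀), where T′ is noncentral t with n − 1 degrees of freedom and noncentrality d√n. For n = 20 the noncentrality is 0.20 × √20 = 0.894 on 19 degrees of freedom, and p = 0.342. The same formula gives 0.383 for n = 25 and 0.488 for n = 40.

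**Step 2: at least two of four, all four shifted, independent.** Power = 1 − (1 − p)⁴ − 4p(1 − p)³. For n = 20: 1 − 0.187 − 0.390 = 0.423. For n = 25 it is 0.494 and for n = 40 it is 0.669.

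**Step 3: correlated markers.** Simulation with normal changes, a common correlation and all four shifted by 0.20:

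| Correlation | n = 20 | n = 40 |
|---|---|---|
| 0 (exact) | 42% | 67% |
| 0.5 | 41% | 59% |
| 0.8 | 38.5% | 54% |
| 0.99 | 35% | 50% |

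**Step 4: a bound that needs no correlation.** The expected number of significant markers is 4p. By Markov's inequality, P(at least two) ≤ 4p/2 = 2p. For n = 20 this is 2 × 0.342 = 0.684. For n = 25 it is 2 × 0.383 = 0.77. Both are below 0.80 whatever the dependence.

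**Step 5: only two of the four shift.** This is all that the hypothesis requires. The other two markers reject at 0.10. Under independence, power for at least two significant results is 0.207 (n = 20) and 0.336 (n = 40). The any-dependence ceiling for n = 20 is (2 × 0.342 + 2 × 0.10)/2 = 0.442. At common correlations of 0.5 to 0.8 simulation gives about 25% to 26% (n = 20) and 36% to 39% (n = 40).

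**Step 6: what 80% would need** (one-sided 0.10; all four shifted for the two-of-four rule):

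| | Two of four, independent | Two of four, correlation 0.8 | One biomarker |
|---|---|---|---|
| d at n = 20 | 0.34 | 0.44 | 0.49 |
| d at n = 40 | 0.24 | 0.31 | 0.34 |
| Pairs at d = 0.20 | 57 | not computed | 114 |

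**Attempts to recover 80% at n = 20 and d = 0.20.** Alpha of 0.05, 0.10 or 0.20, one- or two-sided, did not give it for a single marker or for two of four. The closest two-of-four value was 71%, at one-sided 0.20. At the stated alpha the only nearby figure is for a different rule: at least *one* of four, independent, is 1 − (1 − 0.342)⁴ = 81.3%. That may be where the number came from, but this is inference. It falls to about 65% at correlation 0.5.

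**The case against.** The arithmetic itself is hard to contest, and the obvious escapes fail. The at-least-one-of-four rule is not the one written. Measuring d against the baseline SD would give 80% on the two-of-four rule only with a pre-post correlation a little over 0.8, and the paragraph's own definition of d excludes that reading.

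The better objections concern scope:

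- **The 35% to 42% range is conditional.** It assumes that all four markers shift by 0.20 with a common non-negative correlation. That stands. What needs no such assumption is the 68% ceiling, which is enough to rule out 80%.
- **The pooled sample is larger than 40.** Analysis is by intention to treat and 50 patients are planned. With all 50 pooled, two-of-four power at d = 0.20 is 75.6% if independent. That is a fair point about the pooled analysis, but it does not support a statement made for n = 20.
- **The n = 40 sentence is ambiguous.** It is reversed only if it refers to the detectable effect, which falls as n grows. If it refers to the effect that will be observed, it is merely unsupported. It should not be counted as a second error.
- **This is a pilot, and the paired t-test is only a proxy** for the Kolmogorov–Smirnov and median tests named in the section. Pilot status can justify low power. It does not justify a power figure that is wrong for the test and rule stated.

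**Conclusion.** The concern holds and must be fixed. On the plan's own inputs the stated 80% is unattainable: 34% for one biomarker, and at most 68% for two of four under any dependence. If all four markers truly shift by d = 0.20, 20 per dose misses the success criterion in about 58% to 65% of trials (correlation 0 to 0.99), against the 20% implied. Pooling 40 misses it in about 33% to 50% over the same range. If only two markers shift, power at n = 20 is about 21% (independent) and at most 44%.

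The single-marker and independent figures are exact for normally distributed differences. The correlated figures are simulated under a common correlation, which is an assumption because the documents give none. The conclusion that 80% is wrong does not depend on that assumption.

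**What to change.** Replace the power sentence and the n = 40 sentence, keeping enrolment as it is. For example:

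> Power is for a paired t-test at one-sided 0.10, assuming all four markers shift by the same d. The correlation between marker changes is not known and is assumed to lie between 0 and 0.8. With 20 patients per dose, power at d = 0.20 for at least two of four biomarkers is about 38.5% to 42% (34% for a single biomarker); 80% power requires d of about 0.34 (independent) to 0.44 (correlation 0.8), or 0.49 for a single biomarker. With 40 patients combined, power at d = 0.20 is about 54% to 67% (49% for a single biomarker); 80% power requires d of about 0.24 to 0.31, or 0.34 for a single biomarker. If only two of the four shift by d = 0.20, power is about 21% (n = 20) and 34% (n = 40) with independent markers.

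The text should also say why 20 per dose is used when 25 are randomized; if 20 is an allowance for dropout, state it as such.

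The cost is protocol wording only: no extra patients, procedures or analyses. The stated power becomes less favourable, and the assumed correlation has to be declared.

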- Have no plans to alter antiretroviral therapy, diet or exercise or initiate structured/strategic antiretroviral treatment interruptions.
- Documentation of an HIV-1 RNA level of ≤ 400 copies/mL in the last 4 months prior to study entry
- Age at least 18 years

-Able to swallow pills.

-No diarrhea or nausea/vomiting for the last month

EXCLUSION CRITERIA

All candidates meeting any of the exclusion criteria at baseline will be excluded from study participation.

Pregnancy/lactation

Presence of inflammatory condition (besides HIV) in the last month

Regular use of agents that may affect inflammation in the last 3 months. The regular use of NSAIDS, aspirin, or statins will be allowed as long as dose has been stable for the last 3 months and is not expected to change during the study.

Presence of active neoplastic diseases requiring chemotherapy and/or use of immunosuppressive drugs

Consuming supplements containing more than the DRI level of nutrients known to affect the immune response, i.e. vitamins E, C, B6, selenium, zinc, or β -carotene and unwilling to stop.

BMI <18 kg/m².

Known cardiovascular disease

Uncontrolled diabetes

Allergy or intolerance to zinc sulfate.

Hospitalization within the previous 28 days.

Alcohol or recreational drug use which interferes with compliance

Inability or unwillingness of the individual or legal guardian/representative to give written informed consent

-Any of the following laboratory findings obtained within 14 days prior to the screening evaluation including the following:

-AST and ALT > 2.5 x ULN

-Hemoglobin < 9.0 g/dL

-GFR <50 mL/min

STUDY DESIGN

This is a pilot open labeled randomized double arm study. The duration of the study will be 16 weeks. The total sample size is 50 patients, 25 patients will be randomized to one (45 mg) capsules and 25

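### The only planning statement for the pooled analysis (n = 40) rests on d = 0.20, an effect the design cannot detect with 80% power

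*Combined protocol and SAP*

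**What the plan says.** The effect size paragraph of the Statistical Considerations sets the scale: "The amount of shift or effect size will be measured using Cohen's d value", defined there as the mean difference divided by the SD of the differences. It then makes two planning statements.

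- **Each dose:** "The sample size of 20 achieves 80% power to detect effect size" (Cohen's d) "of 0.20 or higher using a paired t-test with a 0.10 one-sided significance level", "in at least two biomarker out of the four".
- **Both doses, n = 40:** "both doses combined), the estimated effect size should be higher than the threshold Cohen's" d, given as 0.20.

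The second statement carries no power, no detectable effect and no assumed effect for either dose. No other section plans the pooled analysis. The Study Design section says "The total sample size is 50 patients, 25 patients will be randomized to one (45 mg) capsules and 25" to two capsules, so the 20 and 40 in the power text imply a 20% loss (10 of 50), although no dropout rate is stated.

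**The concern.** A power paragraph should tell the reader which effect the analysis can find and with what probability. For the pooled data set, the largest in the trial, the reader gets only an expectation that the estimate will be above 0.20. In a trial without placebo, within-patient change carries the conclusion about zinc, so the sensitivity of that data set matters. A reader who takes 0.20 as an effect the pooled analysis can reliably detect would overestimate its sensitivity. The sentence also follows an n = 20 statement that does not reproduce, and leans on the same 0.20.

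**Working it through.** **Inputs, all from the effect size paragraph unless noted.** Paired t-test; one-sided alpha 0.10; n = 20 per dose and n = 40 pooled; d = 0.20; success in at least two of four biomarkers. Power of 80% is stated for n = 20 only; I carry it over to n = 40 as an assumption. Total randomised is 50 (Study Design). The preliminary data are baseline SDs ("In the statin study the baseline mean (SD) of hs-CRP, log(sCD14), log(sTNF-RI), and LBP are" the figures listed there). No SD of within-patient differences and no correlation between biomarkers is given, so I work in units of d.

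**Formula.** Power = P(T > t(0.90, n−1)), where T is non-central t with n−1 degrees of freedom and non-centrality d√n. Normal check: detectable d ≈ (1.2816 + 0.8416)/√n = 2.1232/√n.

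**Step 1. The plan's own figure (n = 20).** Non-centrality is 0.20 × √20 = 0.894 and the critical value is 1.328. Power is 34.2% per biomarker, not 80%. The d with 80% power is 0.485 (normal check 2.1232/4.472 = 0.475). With four independent, truly shifted markers, power for at least two is 42%. The stated figure does not reproduce.

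**Step 2. The pooled analysis (n = 40), per biomarker.** Non-centrality is 0.20 × √40 = 1.265 and the critical value is 1.304. Power is 48.8%. The d with 80% power is 0.339 (normal check 2.1232/6.325 = 0.336). About 114 pairs would be needed for 80% power at d = 0.20. With all 50 patients the detectable d is 0.303.

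**Step 3. The two-of-four rule at n = 40.** With d = 0.20 in all four markers and independence, power is 1 − 0.512⁴ − 4 × 0.488 × 0.512³ = 1 − 0.0687 − 0.2620 = 0.669. Positive correlation lowers it: by simulation, 61% at 0.3, 59% at 0.5 and 54% at 0.8. The d giving 80% power for at least two markers, by simulation with equal pairwise correlation, is:

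| Markers truly shifted | corr. 0 | 0.3 | 0.6 | 0.9 |
|---|---|---|---|---|
| 4 | 0.24 | 0.26 | 0.29 | 0.32 |
| 3 | 0.29 | 0.31 | 0.32 | 0.34 |
| 2 | 0.39 | 0.39 | 0.39 | 0.37 |

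The range is about 0.24 to 0.39, and every cell is above 0.20. The same grid at n = 20 runs from about 0.34 to 0.56.

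**Step 4. What pooling does to d.** The definition of d contains no n. With equal arms and a common SD within arms, pooled d = ((d₁ + d₂)/2) / √(1 + ((d₁ − d₂)/2)²).

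- 0.20 and 0.20 give 0.20.
- 0.10 and 0.30 give 0.20/√1.01 = 0.199.
- 0 and 0.20 give 0.10/√1.01 = 0.0995.
- 0.20 and 0.30 give 0.25/√1.0025 = 0.2497.

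Pooling roughly averages the two doses and cannot exceed the larger. What it does improve is precision: the standard error, √(1/n + d²/(2n)) at d = 0.20, falls from 0.226 (n = 20) to 0.160 (n = 40).

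**Step 5. 0.20 as a benchmark for the observed d at n = 40.** P(observed d > 0.20) is 50% when the true d is 0.20, and 11% when the true d is 0. The smallest observed d that reaches one-sided 0.10 is 1.304/√40 = 0.206. A benchmark of 0.20 is therefore close to the significance boundary, which is not the same as an effect the test has 80% power to find.

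**The case against.** The best defence is that the sentence is loosely worded, not miscalculated. It contains no arithmetic. Three parts of this defence stand.

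- **A reader might infer that the plan claims d rises because n doubles.** The sentence does not say so. It may follow from the preceding one: if each dose has d of 0.20 or more, with similar SDs, the pooled d is at or above 0.20, as Step 4 shows. It may also be a benchmark for the observed value. On either reading, the absence of n from d contradicts nothing.
- **A reader might infer that a pooled d above 0.20 is a success rule.** No section makes it one. Inference rests on the Kolmogorov–Smirnov and median tests, the intercept-only regression, McNemar's test and a 90% interval for the difference in proportions. That a cut-off placed at the true value is passed about half the time is true of any such cut-off, and is not a defect peculiar to this design.
- **The figures 0.34 and 49% are for one biomarker.** The plan's criterion is two of four, under which power at d = 0.20 can reach about 67%.

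The defence does not supply a justification. If both doses are assumed to have d of at least 0.20, the sentence restates an assumption and says nothing about sensitivity. If 0.20 is a benchmark, its operating characteristics are not given. If a detectable effect was meant, the direction is reversed. The two-of-four rule still leaves power below 80% at d = 0.20. It is also fair that the n = 20 sentence is the root error; for that reason the two should be corrected together.

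**Conclusion.** The concern holds in a limited form: the only planning statement for the pooled analysis does not justify it on any reading. For one-sided 0.10 and n = 40, power at d = 0.20 is 49% per biomarker, against about 67% for two of four in the most favourable case examined (all four shifted, independent). Power of 80% needs d of about 0.34 per biomarker, or about 0.24 to 0.39 under the two-of-four rule.

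These figures assume normally distributed differences, 80% as the target at n = 40, and, for the two-of-four range, equal effects in the shifted markers with pairwise correlations from 0 to 0.9. They apply to the paired t-test named in the power text, not to the other planned tests.

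The pooled analysis remains valid. What fails is its stated sensitivity. In a pilot this calls for a correction of wording, not a redesign.

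**What to change.** Correct the n = 20 and n = 40 sentences together. Changing only the second would leave 80% power at d = 0.20 with 20 patients beside 49% with 40. Suggested content:

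- With a one-sided 0.10 paired t-test, 80% power per biomarker needs d of about 0.49 at n = 20 and 0.34 at n = 40. Power at d = 0.20 is 34% and 49%.
- For at least two of four biomarkers at n = 40, 80% power needs d of about 0.24 (all four shifted, independent) to 0.39 (only two shifted). State the number of shifted markers and the correlation assumed.
- Pooling does not by itself raise d, which is roughly the average over the two doses. It reduces the standard error from about 0.23 to 0.16.
- Drop the word threshold, and report the pooled d with its confidence interval.

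The cost is a less favourable stated sensitivity. No patients, visits or assays are added.
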